1.4 Sample Size Justification

The proposed sample size has been determined to provide adequate statistical power for the co-primary study objectives related to the copayment reduction intervention. The co-primary objective determines whether patient copayment reduction leads to greater persistence to P2Y₁₂ receptor inhibitor therapy at one year after hospital discharge. The hypothesis underlying this objective is that reducing patient copayment in a contemporary population of AMI patients will result in a significant increase in persistence to P2Y₁₂ receptor inhibitor therapy at one year, when compared with usual care. An increase of 4% in the persistence to P2Y₁₂ receptor inhibitor therapy would be considered a clinically important difference[1]. To achieve this objective with a patient-level randomization design, a sample size of 5392 patients would provide greater than 90% power with a two-sided Type I error rate of 0.05. A sample size of 4622 patients would provide greater than 85% power under the same assumptions. These power calculations are based on the assumption that the expected one-year persistence rate in the control group is 70%[1]. These calculations are based on the two group continuity corrected chi-square test statistic and assume that all observations are independently distributed. However, the sample size needs to be adjusted due to the cluster randomized design. We have applied the method described by Eldridge et al. [2] which accounts for the coefficient of variation (CV) of cluster

Statistical Analysis Plan

size and the intra-cluster correlation (ICC). Based on prior multicenter studies, we anticipate an ICC for this endpoint of approximately 0.025. Assuming a total of 300 sites randomized (1:1) with an average sample size of 36.67 patients per site and a CV of 0.65 would yield a design effect of approximately 2.28. The CV of 0.65 has been suggested by others and can be guided by providing minimum and maximum enrollment at the site level [2]. Therefore, a total sample size of 11,000 patients enrolled at 300 sites would result in an effective sample size of 4827 and be sufficient to provide between 85% and 90% power to detect an absolute 4% difference between treatment groups in the cluster randomized design.

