3.1 Non-persistence with antiplatelet therapy at 1 year

The co-primary endpoint of long-term non-persistence will be assessed using patient-reported medication non-persistence. Permanent and temporary discontinuation of a P2Y₁₂ receptor inhibitor will be queried at each follow-up interview. For patients with missing patient-reported medication information, pharmacy fill data will be used to ascertain persistence. Patients who have continued P2Y₁₂ receptor inhibitor use at one year from discharge with less than 30

Statistical Analysis Plan

continuous days of interruption will be considered persistent. We will use the last observation carried forward (LOCF) method for patients who died before one year or had missing 1 year P2Y₁₂ status.

The co-primary objective determines whether patient copayment reduction leads to higher long-term persistence with antiplatelet therapy at one year. The study endpoint for this objective is the proportion of patients at one year who had an interruption ≥ 30 days of P2Y₁₂ receptor inhibitor. The primary analysis will be a logistic regression model with parameters estimated using generalized estimating equations (GEE) to account for within hospital clustering and adjustment for selected patient characteristics (Section 8.3.1) which includes a propensity score for intervention (Section 8.3.2). The propensity score will be estimated using a logistic regression model for intervention group. Categorical variables will be included as sets of indicator variables. Continuous variables will be included assuming a simple linear relationship. Balance of covariates between intervention and usual care arms will be assessed using standardized differences as recommended by Austin [6]. We will assess functional form and possible transformations of the propensity score to be included in the outcome model. Cluster heterogeneity will be quantified using ICCs calculated from unadjusted and adjusted models. We will calculate the ICCs across all hospitals and also by treatment group.

After Steering Committee consensus, the randomization scheme was changed from 1:1 to 2:1 Usual Care vs. Intervention effective November 16, 2015. Randomization schema was added as a covariate for adjustment as shown in Section 8.3.1 and to the propensity model as shown in Section 8.3.2.

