3.2 MACE

The primary study objective evaluates whether patient copayment reduction leads to lower risk of MACE at one year. MACE is defined as the composite of all-cause death, recurrent myocardial infarction, and stroke. Follow-up will be censored at time of study withdrawal or last known alive. The time-to-first MACE event up to one year post-discharge will be compared between intervention and control arms. Cumulative incidence rates will be presented as Kaplan-Meier curves and in tables for 30 days, 6 months, and 1 year post-discharge. The primary analysis will be a Cox proportional hazards model accounting for within hospital clustering using robust standard errors and adjustment for selected patient characteristics (Section 8.3.1) which includes a propensity score for intervention. We will use the same propensity score described in section 3.1. Cluster heterogeneity will be quantified using ICCs calculated from unadjusted and adjusted models. We will calculate the ICCs across all hospitals and also by treatment group.

After Steering Committee consensus, the randomization scheme was changed from 1:1 to 2:1 Usual Care vs. Intervention effective November 16, 2015. Randomization schema was added as a covariate for adjustment as shown in Section 8.3.1 and to the propensity model as shown in Section 8.3.2.

4. Secondary Endpoints

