6.1 Non-persistence with antiplatelet therapy at 1 year

Propensity matched analysis: Within each of the four randomization strata defined, using medians across potential sites from survey conducted prior to ARTEMIS, by high (≥ 400) vs. low (< 400) annual site AMI volume and high ($\geq 15\%$) vs. low ($< 15\%$) proportion of ticagrelor use and by randomization scheme (2:1 vs. 1:1), we will match intervention arm patients to usual care patients. Matching within randomization scheme and strata forces matches across sites of similar size and proportion ticagrelor use and time of site randomization. To run the computerized

Statistical Analysis Plan

matching of intervention to usual care patients, we will utilize the gmatch macro publicly available from the Mayo Clinic Division of Biomedical Statistics and Informatics website of locally written SAS macros. This macro was downloaded on 5/13/13 from the following website: <http://mayoresearch.mayo.edu/mayo/research/biostat/sasmacros.cfm>. The gmatch macro performs greedy matching of cases to controls (intervention patients to usual care patients) within a pre-specified caliper. Greedy matching starts by creating two pools of patients; 1 pool for intervention patients and 1 pool for usual care. Each pool is randomly sorted, then for each intervention patient, we select the first usual care patient in the randomly sorted pool that has a propensity score within the pre-specified caliper. Once a match is made, it is never broken even if another closer match exists. Patients will be matched based on the propensity for intervention group using the propensity score estimated in the primary analysis. If there are no usual care patients with a propensity score within the caliper of a given intervention patient then that intervention patient is not included in the matched sample. We will match on the logit of the propensity score and use a caliper with a width of 0.2 times the standard deviation of the logit of the propensity score as suggested by Austin [7]. To estimate the intervention effect on non-persistence among the propensity matched sample we will fit a logistic regression model stratified by matched pair. Matching on the propensity score is expected to reduce most of the observed differences in patient case mix between the two groups so further adjustment is not necessary.

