Random Intercepts for Hospital: We will fit a logistic regression model with adjustment for the same selected patient characteristics and same propensity score as in the primary analysis. The only modification is that we will account for within hospital clustering using random intercepts for hospitals instead of GEE.

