6.2 MACE

Propensity matched analysis: We will use the same matched sample described in section 6.1 to estimate the intervention effect on MACE using a Cox proportional hazards model stratified by matched pair.

Random Intercepts for Hospital: We will fit a Cox proportional hazards model with adjustment for the same selected patient characteristics and same propensity score as in the primary analysis. The only modification is that we will account for within hospital clustering using random intercepts for hospitals instead of robust standard errors.

7. References

2. Eldridge, S.M., D. Ashby, and S. Kerry, *Sample size for cluster randomized trials: effect of coefficient of variation of cluster size and analysis method*. Int J Epidemiol, 2006. **35**(5): p. 1292-300.
4. Ho, P.M., et al., *Multifaceted intervention to improve medication adherence and secondary prevention measures after acute coronary syndrome hospital discharge: a randomized clinical trial*. JAMA Intern Med, 2014. **174**(2): p. 186-93.
6. Austin, P.C., *Balance diagnostics for comparing the distribution of baseline covariates between treatments groups in propensity-score matched samples*. Statistics in Medicine, 2009. 28: p. 3083-3107.
7. Austin, P.C., *Some methods of propensity-score matching had superior performance to others: results of an empirical investigation and Monte Carlo simulations*. Biometrical Journal, 2009. 51: p. 171-184.

8. Appendices

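### The propensity-matched analyses of both co-primary endpoints (SAP 6.1 and 6.2) make no allowance for hospital clustering, so their tests run at roughly 1.5 to 4 times the nominal 5% level

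*SAP*

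**What the plan says.** Section 6 of the SAP sets out two secondary analyses for each co-primary endpoint: a propensity-matched analysis and a random-intercept model.

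- **Matched, non-persistence (6.1):** "To estimate the intervention effect on non-persistence among the propensity matched sample we will fit a logistic regression model stratified by matched pair".
- **Matched, MACE (6.2):** the same matched sample is used "to estimate the intervention effect on MACE using a Cox proportional hazards model stratified by matched pair".
- **How pairs are formed (6.1):** within site AMI-volume and ticagrelor-use strata and within randomization scheme. In the SAP's words, "Matching within randomization scheme and strata forces matches across sites of similar size and proportion ticagrelor use and time of site randomization".

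The main models of the same endpoints each name a method for hospital:

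- **Primary, non-persistence (3.1):** "parameters estimated using generalized estimating equations (GEE) to account for within hospital clustering".
- **Primary, MACE (3.2):** "Cox proportional hazards model accounting for within hospital clustering using robust standard errors".
- **Random-intercept analysis (6.1):** "we will account for within hospital clustering using random intercepts for hospitals instead of GEE". Section 6.2 has the equivalent for the Cox model.

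Section 2.3 commits to population-averaged methods for clustering, but only as the primary approach. It does not extend to the pair-stratified models, which are conditional on the pair.

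**The concern.** The hospital is the unit of randomization, so a pair of one intervention and one usual-care patient cannot come from a single hospital. Conditioning on the pair therefore does not condition on the hospital. Outcomes of patients at one hospital stay correlated, and that correlation passes to every pair the hospital contributes to. A conditional logistic or pair-stratified Cox model with its default variance counts those pairs as independent, so its standard error is too small.

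The SAP itself treats this correlation as material. For persistence, Section 1.4 states that its assumptions "would yield a design effect of approximately 2.28", and it enlarges the trial accordingly.

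At stake is how the matched results will be read. They are pre-specified secondary analyses of both co-primary endpoints and will be set beside the primary results as support or contradiction. An interval that is too narrow can give false reassurance, or a disagreement that is only noise.

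**Working it through.** **Inputs (SAP 1.4 and 2).** 11,000 patients at 300 sites, so m = 11,000/300 = 36.67; CV of cluster size 0.65; ICC 0.025 (persistence) and 0.01 (MACE); two-sided 5% tests.

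**Step 1: reproduce the plan's figures.** Design effect DE = 1 + [(CV² + 1)m − 1] × ICC, with CV² + 1 = 1.4225.

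- Persistence: 1 + (1.4225 × 36.67 − 1) × 0.025 = 2.279. Effective N = 11,000/2.279 = 4827, as stated.
- MACE: 1 + (1.4225 × 36.67 − 1) × 0.01 = 1.512. Effective N = 7277, against 7278 stated.

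**Step 2: true size when hospital is ignored, full planning clusters.** Size = 2 × [1 − Φ(1.96/√DE)].

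- Persistence: √2.279 = 1.510; 1.96/1.510 = 1.298; size 0.194, or 3.9 times nominal. Interval width is 1/1.510 = 66% of the correct width, and coverage is about 81%.
- MACE: √1.512 = 1.229; 1.96/1.229 = 1.594; size 0.111, or 2.2 times nominal. Width is 81% of correct, and coverage is about 89%.

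**Step 3: allow for patients lost in matching.** Pairing drops surplus usual-care patients, mainly from the 2:1 period, and intervention patients with no match within the caliper. The SAP gives neither the matched fraction nor the final site split, so both are assumed here: 120 intervention and 180 usual-care sites, with 80% or 50% of intervention patients matched. The two arms' design effects are averaged.

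| Intervention patients matched | Mean cluster, intervention / usual care | DE, persistence | Size | DE, MACE | Size |
|---|---|---|---|---|---|
| 80% | 29.33 / 19.56 | (2.018 + 1.670)/2 = 1.844 | 0.149 | (1.407 + 1.268)/2 = 1.338 | 0.090 |
| 50% | 18.33 / 12.22 | (1.627 + 1.410)/2 = 1.518 | 0.112 | (1.251 + 1.164)/2 = 1.207 | 0.075 |

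**Step 4: simulate the tests that the SAP names.** 4,000 replicates per scenario under no effect, with gamma cluster sizes, beta site-level risks and random cross-hospital 1:1 pairs. The pair-conditional logistic and pair-stratified Cox tests were each run with the default variance and with a two-way hospital-robust variance on the same pairs.

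| Sites, intervention / usual care | Intervention patients matched | Non-persistence: default | Robust | MACE: default | Robust |
|---|---|---|---|---|---|
| 150 / 150 | as many as possible | 0.186 | 0.058 | 0.096 | 0.051 |
| 120 / 180 | as many as possible | 0.193 | 0.061 | 0.092 | 0.056 |
| 100 / 200 | as many as possible | 0.160 | 0.060 | 0.090 | 0.059 |
| 120 / 180 | 80% | 0.150 | 0.060 | 0.088 | 0.057 |
| 120 / 180 | 50% | 0.112 | 0.055 | 0.073 | 0.061 |

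The Monte Carlo standard error of the default-variance sizes is at most about 0.006. A separate set of runs gave about 18–20% and 10–11% at full cluster size, and about 10–15% and 7.5–9% with 50–80% matched.

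**Step 5: allow for a smaller residual ICC.** As an illustration only, at full cluster size an ICC of 0.015 for persistence gives DE 1.767 and size 0.140. An ICC of 0.005 for MACE gives DE 1.256 and size 0.080.

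**The case against.** The strongest reply is that the matching is not blind to site. Pairs share AMI-volume stratum, ticagrelor stratum and randomization scheme, and the propensity model (8.3.2) includes bed size, teaching status, government ownership, network membership and surgical capability. Matching on these can remove the part of the between-hospital variance that they explain, and discarding patients shrinks the clusters. Both points stand. They make the 19% and 11% figures upper planning values, and it would be wrong to say that pairing removes none of the hospital variance. Variation between hospitals within a stratum remains, however, and inflation persisted in every scenario tried.

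Four stronger readings are tempting but not supported:

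- **The SAP waives clustering.** The closing remark in 6.1, "so further adjustment is not necessary", follows a statement about patient case mix. It concerns covariates and says nothing about variance. The problem is that no hospital method is given, not that one is refused.
- **Every other analysis handles hospital.** The exploratory and instrumental-variable analyses in 4.13 state no clustering method. The contrast holds for the primary and random-intercept models.
- **The error is uniformly two to four times nominal.** For MACE, the tabulated simulations gave 1.5 to 1.9 times.
- **The trial's conclusions are at risk.** The primary tests account for hospital, no stated decision rule depends on the matched result, and the table shells reserve no output for it.

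**Conclusion.** Wrong as written, and should be fixed. Followed literally, Sections 6.1 and 6.2 give confidence intervals that are too narrow and p-values that are too small for both co-primary endpoints. True size is up to about 19% for non-persistence and 11% for MACE if the planning clusters carry into the matched sample. It is about 10–15% and 7–9% if 50–80% of intervention patients are matched. Overall that is roughly 1.5 to 4 times nominal.

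The figures rest on the SAP's assumed ICCs and CV, and on my assumptions about the matched fraction and site split. A lower residual ICC would reduce them further. They describe each matched analysis separately and are not a trial-wide error rate. The primary GEE and robust Cox analyses, and the sample size, are unaffected.

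**What to change.** State in 6.1 and 6.2 that standard errors, intervals and p-values from the matched sample account for hospital. Either route is adequate:

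- **Smaller change.** Keep the pair-stratified logistic and Cox models, and replace the default variance with a two-way hospital-robust sandwich variance (clustering on both the intervention and the usual-care hospital of each pair), or with a bootstrap that resamples whole hospitals. In the simulation, the sandwich variance returned the error to about 5–6% for both endpoints.
- **Larger change.** Analyse the matched sample with hospital-clustered GEE logistic regression and with Cox regression using hospital-robust standard errors. This is in line with the primary models, but for non-persistence it changes the estimand from a pair-conditional to a marginal odds ratio, and the text should say so.

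Extra stratum or scheme covariates are not needed to repair the variance, because the matching already fixes both. The cost is a sentence or two in each section, slightly more programming and wider intervals. No new data are needed.

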ARTEMIS is a prospective cluster-randomized clinical trial that will evaluate whether patient copayment reduction significantly influences antiplatelet selection and long-term adherence. This study will also examine patient outcomes and the overall cost of care after AMI. After IRB approval, sites will be randomized to either the intervention or the control. Randomization will be stratified by annual site AMI volume and proportion of ticagrelor use using medians across potential sites as cut-offs for identifying high vs. low categories. Approximately 11,000 patients with STEMI or NSTEMI will be enrolled at approximately 300 hospitals.

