8.3 Appendix: List of Adjustment Variables

8.3.1 Adjustment Variables for Primary Models

Variable	Variable Type
Intervention	Yes/no
Randomization scheme	Categorical (2:1 vs. 1:1 scheme)
Interaction* between intervention and randomization scheme	Categorical
Site MI volume	Categorical (high vs. low)
Site % Ticagrelor use	Categorical (high vs. low)
Age	Continuous
Male gender	Yes/no
Race	Categorical (white vs. nonwhite)
Insurance Payors	Categorical (private vs. non-private)
Region	Categorical (Northeast, West, South, vs. Midwest)
Propensity for intervention	Continuous

*We will test for significant interaction and will drop if the interaction term is not significant.

Statistical Analysis Plan

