8.3.2 Variables for Propensity Score Model

[figure not shown]
Variable	Variable Type
Randomization scheme	Categorical (2:1 vs. 1:1 scheme)
Age	Continuous
Age >=65 vs. <65	Yes/no
Male gender	Yes/no
Race	Categorical (white vs. nonwhite)
Ethnicity	Categorical (Hispanic vs. non-Hispanic)
Insurance Payors	Categorical (private vs. non-private)
Prior MI	Yes/no
Prior PCI	Yes/no
Prior CABG	Yes/no
Prior stroke/TIA	Yes/no
Prior Heart failure	Yes/no
Dialysis	Yes/no
PAD	Yes/no
Hypertension	Yes/no
Diabetes	Yes/no
Current/recent smoker	Yes/no
Weight	Continuous
Transfer in	Yes/no
STEMI	Yes/no
Home P2Y ₁₂ inhibitor	Yes/no
Home aspirin	Yes/no
Creatinine Clearance	Continuous
Nadir hemoglobin	Continuous
Multivessel disease	Yes/no
Access Site	Categorical (Femoral vs. other)
PCI performed	Categorical (multivessel vs. culprit vs. none)
CABG performed	Yes/no
Drug-eluting stent implanted	Yes/no
In-hospital or prior bleeding	Yes/no
In-hospital MI	Yes/no
In-hospital stroke	Yes/no
Cardiogenic shock (Killip IV on presentation or in-hospital cardiogenic shock)	Yes/no
Heart failure (Killip II/III on presentation or in-hospital heart failure)	Yes/no
Cardiac Arrest	Yes/no
Cardiac Rehab Referral	Yes/no
Health Literacy	Yes/no (score >=10 vs. <10)
Baseline angina frequency	Categorical (100 vs. 70-90 vs. 0-60 points)
Baseline PHQ2>3	Categorical
Baseline EQ5D VAS	Continuous

Statistical Analysis Plan

Married	Yes/no
Employed	Yes/no
Education (college graduate)	Yes/no
Baseline financial hardship	Categorical (1 vs. 2/3 vs. 4/5)
Missed >1 dose of medication in the last month	Yes/no
Site: Total bed size	Continuous
Site: Teaching Status	Yes/no
Site: Government hospital	Yes/no
Site: Member of a Healthcare Network	Yes/no
Site: Surgery Capabilities	Yes/no

[figure not shown]

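### The propensity-matched analyses in SAP 6.1 and 6.2 leave Region uncontrolled, although the other specified adjusted analyses of the co-primary endpoints adjust for it

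*SAP*

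**What the plan says.** Section 8.3.1 lists the covariates of both primary models. Region is one of them, with four levels ("Categorical (Northeast, West, South, vs. Midwest"), alongside the propensity score.

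Section 8.3.2 lists the variables of the propensity model. Its hospital-level entries run from "Site: Total bed size" through teaching status, government hospital and "Site: Member of a Healthcare Network" to surgery capabilities. Region does not appear.

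Section 6.1 reuses that score for matching: "Patients will be matched based on the propensity for intervention group using the propensity score estimated in the primary analysis". Matching is done within cells of AMI volume, ticagrelor share and randomization scheme, of which the SAP says: "Matching within randomization scheme and strata forces matches across sites of similar size and proportion ticagrelor use and time of site randomization". The outcome model is a logistic regression stratified by matched pair. No covariates are added, because matching is "expected to reduce most of the observed differences in patient case mix between the two groups so further adjustment is not necessary".

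Section 6.2 carries this over to the other co-primary endpoint: "We will use the same matched sample described in section 6.1 to estimate the intervention effect on MACE". It uses a Cox model stratified by pair and names no covariates.

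On the design, the introduction says: "Randomization will be stratified by annual site AMI volume and proportion of ticagrelor use". Region was not a stratification factor.

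**The concern.** Leaving Region out of the score does no harm in the primary models, where it enters as a separate covariate. It matters once the score is used on its own, as in the matched analyses. Two other hospital factors missing from the score, AMI volume and ticagrelor share, come back through the matching cells. Region does not.

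The reason given for adding no covariates concerns patient case mix. Region is a property of the hospital, and hospitals were the units randomized. With whole hospitals allocated and no stratification by region, a visible difference in regional make-up between arms can easily arise by chance. The matched analyses would leave it in the estimate, so a gap between matched and primary results could partly reflect Region.

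The planned tables would show this only in part. Table 1 gives Region by arm for sites, but Tables 2a and 2b omit it. Section 3.1 promises standardized differences without naming Region or the matched sample.

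**Working it through.** **Step 1: which primary-model covariates do the matched analyses control?**

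| Covariate in 8.3.1 | In the 8.3.2 score | Matching cell in 6.1 |
|---|---|---|
| Randomization scheme | yes | yes |
| Site MI volume | no | yes |
| Site ticagrelor use | no | yes |
| Age, sex, race, insurance | yes | no |
| Region | **no** | **no** |

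The remaining 8.3.1 entries are the intervention, its interaction with scheme (dropped if not significant) and the score itself. None of these is a baseline factor to balance. Region is the only one left over.

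**Step 2: the plan's own precision figures (SAP 1.4).** The inputs are 300 sites, 11,000 patients, 36.67 per site, CV 0.65 and ICC 0.025.

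- Design effect = 1 + ((0.65² + 1) × 36.67 − 1) × 0.025 = 2.279; the SAP gives 2.28.
- Effective sample size = 11,000 / 2.279 = 4827, as stated.

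With persistence of 70% and 74% (mean 72%), the SE of the difference is:

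- 1:1 allocation: √(0.72 × 0.28 × 4 / 4827) = 1.29 points.
- 1:2 allocation: √(0.72 × 0.28 × 4.5 / 4827) = 1.37 points.

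**Step 3: chance imbalance in one region.** Assume the region holds 25% of hospitals. The allocation moved from 1:1 to 2:1 during the trial and the SAP does not give the final split, so 150/150 and 100/200 hospitals bracket it. The SD of the between-arm difference in patient share is √(0.25 × 0.75 × (1 + 0.65²) × (1/k₁ + 1/k₀)):

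- 150/150: √(0.1875 × 1.4225 × 0.01333) = 0.060.
- 100/200: √(0.1875 × 1.4225 × 0.015) = 0.063.

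The SD is thus 6.0 to 6.3 percentage points.

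**Step 4: effect on the non-persistence contrast.** Assume four equal regions with mean non-persistence of 30%. The error SD is the between-region SD × √(1.4225 × (1/k₁ + 1/k₀)). The multiplier is 0.138 for 150/150 and 0.146 for 100/200.

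| Assumed regional rates | Between-region SD | Error SD, 150/150 | Error SD, 100/200 | Share of variance |
|---|---|---|---|---|
| 25/28/32/35% | √14.5 = 3.81 | 0.52 | 0.56 | about 16% |
| 28/29/31/32% | √2.5 = 1.58 | 0.22 | 0.23 | about 3% |

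Each share compares error and SE at the same allocation. For the wider spread it is 0.52²/1.29² or 0.56²/1.37², both about 16%. For the narrower spread it is 0.22²/1.29² or 0.23²/1.37², both about 3%.

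**Step 5: is the wider spread compatible with the plan?** ICC 0.025 implies a between-hospital variance of 0.025 × 0.2016 = 0.00504, or 50.4 squared points. The wider spread would use 14.5 of that, about 29%. That is possible but substantial. The SAP gives no regional rates for either endpoint, so no size is offered for MACE.

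**The case against.** The strongest reply is that little depends on this. Both primary models adjust for Region. The random-intercept models in 6.1 and 6.2 keep the same covariates and change only the handling of clustering. The as-treated analysis in 4.12 uses the methods of 3.1 and 3.2. All of this stands. A reader might infer that the co-primary conclusions are confounded by region, and the documents do not support that.

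Nor is the error systematic bias. Sites were randomized, so regional imbalance is random. The between-hospital variance behind the design effect already contains any regional component. The 3% to 16% is thus a removable share of error already counted, not an addition to it.

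A reader might also infer that the omission defeats the matched analysis as a check. That goes too far. The matched model already differs from the primary in population, in conditional versus marginal effect and in its treatment of clustering. A gap could not be pinned on one cause even with Region controlled.

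The size is soft as well. The regional spreads are assumed. Race, ethnicity, insurance and the hospital variables in the score may correlate with region and remove part of the imbalance. The SE is that of the full sample; the matched sample is smaller and its SE larger, which lowers the share.

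None of this explains why Region alone is dropped, and the reason given in 6.1 does not cover it.

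**Conclusion.** The point holds as an inconsistency confined to the propensity-matched secondary analyses. These are the only specified adjusted analyses of the co-primary endpoints in which chance regional imbalance is uncontrolled. The reading takes the 8.3.2 list as complete as printed.

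For non-persistence, the avoidable error has an SD of about 0.2 to 0.55 points against a target difference of 4 points, or roughly 3% to 16% of the estimate's variance. This rests on four equal regions, the assumed spreads, the plan's 300 sites and CV of 0.65, and no balance gained through correlated variables. Whether an imbalance exists cannot be known before the data. The sample size, power and significance level in the SAP are unaffected.

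**What to change.** In 6.1 and 6.2, enter Region (four categories) as a covariate in the pair-stratified logistic and Cox models, and amend the statement that no further adjustment is needed. Two alternatives would also do: refit a score that includes Region and use it for matching only, or match within Region. Whichever is chosen, report Region's standardized difference in the matched sample.

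The cost is small. Region is already collected (Table 1), and the covariate option adds three parameters to each model. Matching within Region would lose some pairs, and a refitted score could also change which patients find a match within the caliper.

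Simply adding Region to 8.3.2 looks like the shortest edit but reaches further. That score is a covariate in both co-primary models and serves the secondary endpoints too, so the edit would alter the primary analyses to repair a secondary one. The options above leave the primary-analysis score unchanged.
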